9.3.1. Risk factors

Risk factors (as defined in the nirmatrelvir/ritonavir label²⁶) are as follows:

- Being overweight/obesity (e.g., BMI > 25 kg/m²)
- Older age (e.g., age \geq 60 years)
- Current smokers
- Immunosuppressive disease or immunosuppressive treatment

- Comorbidity
 - Chronic kidney disease
 - Diabetes
 - Cardiovascular disease (including congenital heart disease) or hypertension
 - Chronic lung diseases (e.g., chronic obstructive pulmonary disease, asthma [moderate-to-severe], interstitial lung disease, cystic fibrosis, and pulmonary hypertension)
 - Sickle cell disease
 - Neurodevelopmental disorders (e.g., cerebral palsy, Down's syndrome) or other conditions that confer medical complexity (e.g., genetic or metabolic syndromes, and severe congenital anomalies)
 - Active cancer
 - Medical-related technological dependence not related to COVID-19 (e.g., tracheotomy, gastrostomy, or positive pressure ventilation)

9.3.2. COVID-19 severity

According to the China Guideline on Diagnosis and Treatment Plan for Coronavirus Disease 2019 (9th Edition),¹⁹ COVID-19 severity is categorized as follows:

- Mild illness: Mild signs and symptoms of COVID-19 but no abnormal chest imaging.
- Moderate illness: Showing evidence of signs and symptoms of COVID-19 and abnormal chest imaging.
- Severe illness: Individuals who have oxygen saturation (SpO₂) ≤93% on room air, a ratio of arterial partial pressure of oxygen to fraction of inspired oxygen (PaO₂/FiO₂) ≤300 mmHg, a respiratory rate (RR) ≥30/min, or lung infiltrates progression >50% within 24–48 hours.
- Critical illness: Individuals who have respiratory failure requiring mechanical ventilation, septic shock, or multiple organ dysfunction (MOD).

Note: Different scales and categorization of COVID-19 severity may be used across hospitals in real-world clinical settings, such as the WHO Ordinal Scale.²⁷ If a COVID-19 severity categorization different from the above China guideline is used in one participating site, the participating site's categorization will be collected via eCRF and will be mapped to the above four categories during analysis.

9.3.3. Signs/symptoms of COVID-19

Signs/symptoms of COVID-19 include cough, shortness of breath or difficulty breathing, objective fever (documented temperature >38°C [100.4°F]), fatigue (low energy or tiredness), subjective fever (e.g., feeling feverish), chills or shivering, muscle or body aches, diarrhea, nausea, vomiting, headache, sore throat, stuffy and runny nose.²⁰

Among them, the targeted signs/symptoms of COVID-19 for analysis include cough, shortness of breath or difficulty breathing, subjective fever (e.g., feeling feverish), chills or

shivering, muscle or body aches, diarrhea, nausea, vomiting, headache, sore throat, stuffy and runny nose.²⁰

9.3.4. Development of the Child Pugh score

Table 2. Assignment of the scores based on parameters

Assessment parameter	Score		
	1	2	3
Ascites	None	Mild	Moderate / severe
Encephalopathy (grade)	None	1–2	3–4
Total bilirubin (mg/dL)	<2	2–3	>3
Albumin (g/L)	>35	28–35	<28
Prothrombin time (second prolonged)	<4	4–6	>6
Or International normalized ratio	<1.7	1.8–2.3	>2.3

Table 3. Child Pugh scores correspond with the Child Pugh grades

Child Pugh grade	Child Pugh score	Level of dysfunction
A	5–6	Mild
B	7–9	Moderate
C	10–15	Severe

9.3.5. COVID-19-related treatments

COVID-19-related treatments are defined as any therapy that is approved and used as indicated by regulatory authority (including approvals for emergency use), or any therapy as recommended by a national (or a reputable international) scientific body (e.g., WHO, European Centre for Disease Prevention and Control, Centers for Disease Control and Prevention, or National Institute of Health) for COVID-19 treatment.

Categories of variables for COVID-19-related treatments are as follows:^{19 28}

- Antiviral therapy: Monoclonal antibodies (Amubarvimab/Romlusevimab Combination, bebtelovimab, Casirivimab, Imdevimab, Regdanvimab, Bamlanivimab, Etesevimab, or any other monoclonal antibodies for COVID-19 treatment), COVID-19 Human Immunoglobulin, convalescent plasma, azvudine, remdesivir, and molnupiravir
- Immunotherapy: Glucocorticoid, Interleukin-6 (IL-6) inhibitor (tocilizumab, sarilumab), baricitinib, tofacitinib
- Any other COVID-19 related treatments: Anticoagulant, Traditional Chinese Medicine (TCM) and oxygen supplemental therapies

9.3.6. Adverse event

The observation period of AE with explicit attribution to nirmatrelvir/ritonavir is defined as the period from initiation of nirmatrelvir/ritonavir (i.e., the index date) until discharge from hospital, death, or maximally 28 days after last dose of nirmatrelvir/ritonavir, whichever comes first.

Seriousness of each AE: A SAE is any untoward medical occurrence in a participant or a patient administered a medicinal product at any dose, that:

- Results in death
- Is life-threatening
- Requires inpatient hospitalization or prolongation of hospitalization
- Results in a persistent or significant disability/incapacity
- Results in congenital anomaly / birth defect

Or that is considered to be:

- An important medical event

Medical and scientific judgment is exercised in determining whether an event is an important medical event. An important medical event may not be immediately life-threatening and/or result in death or hospitalization. However, if it is determined that the event may jeopardize the patient or may require intervention to prevent one of the other outcomes listed in the definition above, the important medical event should be reported as serious.

Examples of important medical events are intensive treatment in an emergency room or at home for allergic bronchospasm; blood dyscrasias or convulsions that do not result in hospitalization; development of drug dependency or drug abuse; or development of potential drug-induced liver injury; suspected transmission of an infectious agent.

Each AE's duration: From onset to end date of each AE or till the end of observation period.

Each AE's outcome: Recovered/resolved, recovered/resolved with sequelae, recovering/resolving, not recovered/not resolved, fatal, and unknown.

Actions for each AE: Actions made to manage each AE.

Severity of each AE will be collected.

9.3.7. Time to alleviation of all targeted COVID-19 signs and symptoms

The targeted signs and symptoms of COVID-19 (described in section 9.3.3) will be used for the analysis of time to alleviation calculation. For a patient, the targeted signs and symptoms recorded in either baseline or observation period will be evaluated.

The First Alleviation Date for a targeted sign/symptom is the date when alleviation is firstly recorded in medical records during the observation period

Event Date = The last date of (The First Alleviation Dates for ALL targeted signs/symptoms to be evaluated)

The time to alleviation of all targeted COVID-19 signs and symptoms is defined as:

- For a patient with the Event Date, it will be calculated as (Event Date) – (Index Date) +1.
- For a patient without the Event Date, it will be calculated as (End of Observation Date) – (Index Date) +1 and be considered as a censoring time. ^{7 12}

9.3.8. Time to two consecutive negative SARS-CoV-2 test results / CT ≥ 35

For patients with at least two SARS-CoV-2 tests (specimens collected in two different calendar days) after treatment initiation during observation period, the first day of a negative SARS-CoV-2 test / CT ≥ 35 from two consecutive negative results is considered as an Event Date.

The time to event of two consecutive negative SARS-CoV-2 test results / CT ≥ 35 in this study is defined as:

- For a patient with the Event Date, it will be calculated using (Event Date) – (Index Date) +1.
- For a patient without the Event Date, it will be calculated as (End of Observation Date) – (Index date) + 1 and be considered as a censoring time.

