Patients who initiated nirmatrelvir/ritonavir treatment between 11 February 2022 and 31 August 2022 will be included in this study. For the purposes of analysis, the index date for an individual patient is defined as the date of initiating nirmatrelvir/ritonavir treatment. The baseline period for an individual patient is defined as the period from the first day of hospitalization to the day prior to the index date to capture the patient's baseline clinical characteristics, medical history, and comorbidity. The observation period for an individual patient is defined as the period from initiation of nirmatrelvir/ritonavir (i.e., index date) until discharge from hospital, death, or a maximum of 28 days after the last dose of nirmatrelvir/ritonavir, whichever comes first.

The study data cut-off date will be 02 October 2022. Each patient will be included in the study only once. If the patient initiated nirmatrelvir/ritonavir treatment more than once between 11 February 2022 and 31 August 2022, only the first treatment course will be included for analysis.

Population

Study population will consist of patients who initiated treatment with nirmatrelvir/ritonavir within the period from 11 February 2022 to 31 August 2022 during hospitalization. Approximately 1000 patients are planned to be included in the study. Eligible patients must meet the following inclusion criteria and none of the exclusion criteria:

Inclusion criteria

- Chinese patients aged ≥ 18 years on index date
- Patients initiated and took at least one dose of nirmatrelvir/ritonavir between 11 February 2022 and 31 August 2022 during hospitalization
- Patients had documented confirmed symptomatic COVID-19 with positive SARS-CoV-2 test in any specimen collected prior to or at initiation of nirmatrelvir/ritonavir
- Evidence of a personally signed and dated informed consent document (ICD) indicating that the patient (or a legally acceptable representative) has been informed of all pertinent aspects of the study if requested by study sites.

Exclusion criteria

- Patients participated in any interventional COVID-19 trials during the study period

Variables

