9. RESEARCH METHODS

9.1. Study design

This is a multicenter, single-arm, retrospective observational study to describe the safety, treatment patterns and effectiveness of nirmatrelvir/ritonavir among patients with COVID-19 in China. Approximately 5 hospitals and 1000 patients are planned to be included in this study. Retrospective data abstraction will start after site ethics committee approval. Patients who initiated nirmatrelvir/ritonavir treatment between 11 February 2022 and 31 August 2022 will be included in this study. Continuous recruitment of patients in each site will be employed. For analyzing purpose, the index date for an individual patient is defined as the date of initiating nirmatrelvir/ritonavir treatment. The baseline period for an individual patient is defined as the period from the first day of hospitalization through the index date to capture the patient's baseline clinical characteristics, medical history, and comorbidity. The observation period for an individual patient is defined as the period from initiation of nirmatrelvir/ritonavir (i.e., index date) until discharge from hospital, death, or a maximum of 28 days after the last dose of nirmatrelvir/ritonavir, whichever comes first. The study data cut-off date will be 02 October 2022. Each patient will be included in the study only once. If the patient initiated nirmatrelvir/ritonavir treatment more than once between 11 February 2022 and 31 August 2022, only the first treatment course will be included for analysis. The study design schematic is presented in [Figure 1](#).

Figure 1. Study design schematic

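### Time to alleviation counts targeted symptoms that may have gone before the first dose and, read literally, censors patients who never had one, so the Kaplan-Meier median depends partly on charting habit

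*Protocol*

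**What the plan says.** Protocol section 9.3.7 builds the endpoint in four steps.

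- Symptoms that count: "For a patient, the targeted signs and symptoms recorded in either baseline or observation period will be evaluated".
- Date for each symptom: "The First Alleviation Date for a targeted sign/symptom is the date when alleviation is firstly recorded in medical records during the observation period".
- Event: "Event Date = The last date of (The First Alleviation Dates for ALL targeted signs/symptoms to be evaluated").
- No event: "For a patient without the Event Date, it will be calculated as (End of Observation Date") minus the index date plus 1, treated as a censoring time.

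The baseline period starts at admission. Section 9.1 defines it as the "period from the first day of hospitalization through the index date"; the abstract has the "period from the first day of hospitalization to the day prior to the index date". The observation period runs from the index date "until discharge from hospital, death, or a maximum of 28 days after the last dose of nirmatrelvir/ritonavir, whichever comes first".

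Section 9.3.3 gives a full symptom list and a shorter targeted list. Two entries of the full list are missing from the targeted one: "objective fever (documented temperature >38°C [100.4°F]), fatigue (low energy or tiredness"). Entry (section 9.2) requires symptomatic COVID-19 but neither a targeted symptom nor a symptom present on the index date. EAS1 (section 9.7.1) asks for any one effectiveness variable and a recent positive test; EAS adds severity and a risk factor. Section 9.7.3.2 reports the Kaplan-Meier median with its 95% CI in both sets, with no further restriction for this endpoint.

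**The concern.** Time to alleviation after treatment has a clear meaning only for a patient who has something to alleviate when treatment starts. Section 9.3.7 does not make that a condition. It looks back to admission to decide which symptoms count, but looks only forward from the index date for their alleviation. A symptom that came and went in between is in the set without a natural alleviation date.

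The reported median would then mix the time course of symptoms after treatment with how wards happened to chart symptoms already gone. The study has one arm, so no comparator exists in which the artefact could cancel. Effectiveness is also to be examined by time from symptom onset to first dose (section 9.7.4). Patients who start later have had longer to lose symptoms before dosing, so the artefact may differ between those subgroups. Section 9.7.5 puts every endpoint into the interim analysis, so the rule would be used early.

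**Working it through.** The protocol states no expected median, event rate or precision for this endpoint, so there is no figure to reproduce. The check has two parts.

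**Applying the rule as written**

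1. All targeted symptoms gone before the first dose, nothing charted afterwards: the symptoms are evaluated, none has a First Alleviation Date, there is no Event Date, and the patient is censored while symptom-free.
2. The same patient with an entry of absence on or after the index date: Table 1 abstracts alleviation and severity (including absent) by date, so that entry can be taken as the First Alleviation Date. If it is on the index date, the time is 0 + 1 = Day 1, and resolution before treatment is counted after it.
3. Only objective fever or fatigue ever charted: the set of symptoms to evaluate is empty, no Event Date can arise, and the only rule for that case is censoring.

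The missing-data rule in section 9.7 is worded for continuous and categorical variables, so it does not take these patients out of the Kaplan-Meier analysis. By contrast, the viral clearance endpoint in section 9.3.8 limits its denominator to patients with at least two tests after initiation.

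**Illustration of size**

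Assumptions, none from the documents: patients with a targeted symptom at index have an exponential alleviation time with median m; a share f has none at index; censoring is independent of alleviation; time is treated as continuous.

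- Whole share censored: the curve estimates f + (1 − f)S(t). Setting this to 0.5 gives a median of m × log2[(1 − f)/(0.5 − f)].
- Whole share scored on Day 1: the curve is (1 − f)S(t). Setting this to 0.5 gives a median of m × log2[(1 − f)/0.5].

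For m = 5:

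- f = 10%, censored: 5 × log2(0.9/0.4) = 5 × 1.170 = 5.85 days
- f = 10%, Day 1: 5 × log2(0.9/0.5) = 5 × 0.848 = 4.24 days
- f = 20%, censored: 5 × log2(0.8/0.3) = 5 × 1.415 = 7.08 days
- f = 20%, Day 1: 5 × log2(0.8/0.5) = 5 × 0.678 = 3.39 days

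| Assumed m | f | All censored | All on Day 1 |
|---|---|---|---|
| 5 | 5% | 5.39 | 4.63 |
| 5 | 10% | 5.85 | 4.24 |
| 5 | 20% | 7.08 | 3.39 |
| 7 | 10% | 8.19 | 5.94 |
| 7 | 20% | 9.91 | 4.75 |

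A simulated Kaplan-Meier analysis of 200,000 patients, with independent discharge censoring (median about 8, 12 or 20 days, capped at 33), agrees for m = 5: 5.8 to 5.9 and 7.1 days when censored, 4.2 to 4.3 and 3.4 days on Day 1, for f = 10% and 20%. With f = 0 it returns 5.0.

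The two columns are extremes. If a share c of all patients is censored and f − c scores on Day 1, the median solves S = (0.5 − c)/(1 − f). With c = f/2 this is S = 0.5, and the two errors cancel exactly. The Day 1 column applies only to patients whose symptoms resolved before dosing; those who never had a targeted symptom cannot score on Day 1.

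**The case against.** A reader might infer that all these patients cannot have the event. That goes too far. It holds only for patients with no targeted symptom, and even there only by literal application. No sentence names them, and leaving them out as not evaluable is also a natural reading, which a statistical analysis plan could settle. For patients whose symptoms resolved before dosing, any later note of absence supplies a date. Section 9.4 lists discharge summaries among the sources, so such notes may be common. Where none exists, the problem overlaps with the missing records acknowledged in section 9.9.

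A reader might also take the illustrative medians as the bias to expect. The documents do not support that: median, distribution and share are all assumed, and opposite errors offset in part. The share is limited by the symptomatic entry criterion and by a broad targeted list that includes subjective fever, so a patient with measured fever may well have a targeted symptom charted.

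Finally, the latest of the first alleviation dates can fall while an earlier symptom has come back: cough alleviated on day 3 and back on day 5, headache alleviated on day 6, gives an event on day 6 with cough present. To call this an error would be too strong. It is an explicit, reproducible rule for irregular charts, and any recurrence criterion depends on an assessment frequency the protocol does not control.

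What stands against all this is that section 9.3.7 fixes which symptoms count, which alleviation dates count and what happens without one. A later plan that required a symptom at index would be departing from that text, not filling a gap.

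**Conclusion.** The point holds in limited form. As written, section 9.3.7 lets patients already free of targeted symptoms at the first dose, and on a literal reading patients who never had one, into the Kaplan-Meier risk set. Charting decides whether the former lengthen or shorten the median, so the direction of the bias cannot be known in advance. Its size is also unknown. Under the stated assumptions (5-day exponential median), a 10% share moves the median to somewhere between 4.24 and 5.85 days and a 20% share to between 3.39 and 7.08, with mixtures in between.

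This should be fixed, but it is not critical. The endpoint is one of four secondary effectiveness endpoints in a descriptive study without hypothesis tests. The primary objective is safety, and the precision figures in section 9.5 rest on viral clearance.

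**What to change.** In section 9.3.7:

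- restrict this endpoint to patients with at least one targeted symptom present at the last assessment on or before the index date;
- evaluate only those symptoms plus targeted symptoms that newly emerge afterwards;
- report the number excluded for having none, and the number with no usable index assessment.

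Optionally, add a sensitivity analysis in which the event is the first date on which all evaluated symptoms are recorded as alleviated at the same time.

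The two definitions of the baseline period should be reconciled at the same time, because the restriction needs to say whether an index-day entry counts. The discrepancy does not itself alter the conclusion.

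Cost: a rewording before the interim analysis and a somewhat smaller denominator. Table 1 already collects symptom presence and severity near the index date, and dated alleviation afterwards. The restriction does rely on dated entries around index, which Table 1 does not fully guarantee: the baseline item takes the assessment on or nearest the index date, which could fall after it, and later severity is collected only where available. That is why the count without a usable assessment should be reported.

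### Section 9.3.7 requires alleviation of every targeted symptom recorded since admission, with no onset test or reference level, so stable pre-existing cough or dyspnoea can lengthen the median time to alleviation

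*Protocol*

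**What the plan says.** Protocol section 9.3.7 first limits the endpoint by a label: "The targeted signs and symptoms of COVID-19 (described in section 9.3.3) will be used for the analysis of time to alleviation calculation". It then sets the scope for each patient: "the targeted signs and symptoms recorded in either baseline or observation period will be evaluated". Section 9.1 defines the baseline period as "the period from the first day of hospitalization through the index date". The abstract ends that period one day earlier, but both start it at admission.

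Section 9.3.3 is a list of symptom types: "the targeted signs/symptoms of COVID-19 for analysis include cough, shortness of breath or difficulty breathing", followed by items such as aches, headache and sore throat. It has no condition on onset or on change from the patient's usual state.

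For each symptom the component date is "the date when alleviation is firstly recorded in medical records during the observation period". The composite is "Event Date = The last date of (The First Alleviation Dates for ALL targeted signs/symptoms to be evaluated"). A patient without that date is censored at the end of observation. Table 1 collects alleviation as yes/no by date, with a severity level where available, and refers to section 9.3.7 for the definition of alleviation. Section 9.3.7 supplies a date rule but no threshold.

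Section 9.3.1 lists among the risk factors "Chronic lung diseases (e.g., chronic obstructive pulmonary disease" and related conditions, and cardiovascular disease. Section 9.7.1 requires at least one risk factor for the EAS. Section 9.7.4 names risk factors as a subgroup variable for effectiveness.

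**The concern.** Cough and shortness of breath are targeted symptoms, and they can also be everyday symptoms of the chronic lung and heart diseases named as risk factors. If a usual cough is abstracted as a targeted symptom, it must have an alleviation date before the patient can have an event. A stable symptom has nothing to ease, so the patient is censored even if every COVID-19 symptom has gone.

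For those patients the endpoint would measure persistence of comorbidity and not recovery from COVID-19. The pooled median would move upwards. In a subgroup with chronic lung disease, where the share could be well above average, an apparently slow recovery could be the comorbidity itself.

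**Working it through.** **No figure to reproduce.** The protocol states no expected median, event rate or share with chronic symptoms for this endpoint. The check is therefore of direction and of size over an assumed range.

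**What the text lets an abstractor decide**

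| Question | Where one would look | What is there |
|---|---|---|
| Which symptoms count? | 9.3.3, 9.3.7 | Listed types recorded in baseline or observation |
| Must it be new, or worse than usual? | 9.3.3, 9.3.7 | No condition |
| What level counts as alleviated? | Table 1, referring to 9.3.7 | A date rule, no level |
| Is a pre-illness level collected per symptom? | Table 1 | Not listed; only the onset date of the first COVID-19 symptom |

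**Model.** Inputs, all assumed:
- q: share of patients with a pre-existing targeted symptom.
- r: share of those whose chart still records an alleviation.
- m: median without such patients.
- k: Weibull shape, 1 (exponential) to 2.
- Censoring independent of alleviation.

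The share that can never have an event is q_eff = q(1 − r). The survival curve is

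S(t) = q_eff + (1 − q_eff) × 0.5^((t/m)^k).

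Setting S(t) = 0.5 gives

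t/m = [log2((1 − q_eff)/(0.5 − q_eff))]^(1/k).

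**Upper case, r = 0**
- q = 5%: log2(0.95/0.45) = 1.078; square root 1.038. Factor 1.04-1.08.
- q = 10%: log2(0.90/0.40) = 1.170; square root 1.082. Factor 1.08-1.17.
- q = 20%: log2(0.80/0.30) = 1.415; square root 1.190. Factor 1.19-1.42.
- q of 50% or more: the curve never falls below one half, apart from the exact boundary, so the median is not reached.

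In days, with k = 1 and m = 5, the median becomes 5.4, 5.8 and 7.1 at q = 5, 10 and 20%. With m = 7 it becomes 7.5, 8.2 and 9.9.

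**Half recorded as alleviated, r = 0.5.** Then q_eff is 5% at q = 10% and 10% at q = 20%, so the factors are 1.04-1.08 and 1.08-1.17.

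**All recorded as alleviated, r = 1.** q_eff = 0 and the factor is 1.00.

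**Simulation check.** Kaplan-Meier on whole days, n = 20,000, m = 7, k = 1, discharge median about 14 days, cap 33 days. With no affected patients the median was 7-8 days. With r = 0 it was 9 days at q = 10% and 10 days at q = 20%. With r = 0.5 it was 8 and 9 days. With r = 1 it stayed at 7-8 days. The direction and rough size agree with the formula, within the coarseness of whole days.

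**The case against.** The strongest reply is that the protocol never says chronic symptoms count. Section 9.3.7 and Table 1 speak of signs and symptoms of COVID-19, comorbidities are a separate variable, and abstractors already judge the onset of the first COVID-19-related symptom. This stands in part: inclusion of a usual cough follows from a literal reading and not from an express statement. But the label leads back to a list of types, which gives no test for a usual cough at the approximately 5 hospitals. Where this protocol wants attribution it defines it, as it does for adverse events in section 11.

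Second, alleviation is not resolution. A reader might infer that any patient with chronic cough or dyspnoea can never reach the event. The documents do not support that, because a chronic symptom that worsened and then eased can have an alleviation date. What remains is the stable symptom.

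Third, a reader might infer that starting the baseline at admission brings in symptoms of other admitting illnesses on a large scale. Section 7 says that patients with positive tests are admitted because of the test, so for them the window lies within the COVID-19 episode. Patients infected during another admission are eligible, but their number is not given.

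Fourth, the SAP or the CRF completion guidance may settle this. Either could set a rule, but an analysis plan cannot recover chronicity that was never abstracted.

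Finally, this is a secondary endpoint in a single-arm descriptive study, so no treatment contrast is biased. Counting the first alleviation even if the symptom returns acts in the other direction, towards a shorter median.

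**Conclusion.** The point holds as a conditional risk. Section 9.3.7 states an unqualified rule, and nothing in the protocol tells an abstractor how to treat a symptom that predates COVID-19. Taken literally, that rule can make the Kaplan-Meier median too long. The effect is small at an assumed 5% share and material at 20% if no alleviation is recorded, and it is absent if alleviation is always recorded. The shares, the underlying median and the curve shape are assumptions. The document gives none of them, so it does not show that the median is in fact too long.

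A reader might also infer that the bias must be larger in the EAS than in EAS1, because the EAS requires a risk factor. The documents do not support a direction. Many qualifying factors, such as age, BMI and diabetes, do not imply chronic cough or dyspnoea, and the EAS also drops patients with severe or critical illness at baseline, whom EAS1 keeps. The place where distortion is most plausible is a chronic-disease subgroup under section 9.7.4.

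**What to change.** In section 9.3.7, evaluate only targeted symptoms that began or worsened with the current COVID-19 episode. For a symptom documented before onset, count return to its documented usual level as alleviation.

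Add one CRF field per targeted symptom: present before COVID-19 at the same level, with answers yes, no or not stated. Treat *not stated* as COVID-19 related. Report the present all-symptom rule as a sensitivity analysis, so that the effect of the restriction is visible.

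The cost is a short addition to 9.3.7, one extra abstraction field per symptom and one further Kaplan-Meier run. The field is cheapest to add before abstraction starts, which section 6 plans for 6 March 2023. The downside is that charts silent on chronicity stay under the present rule, so the correction will be partial.
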